Cardiovascular effects will be assessed via blood pressure and pulse measurement. Blood pressure and heart rate will be assessed periodically during each experimental session by an automatic blood pressure and pulse monitor. Blood pressure and pulse will be measured at the outset of the experimental session, once approximately every hour, or as needed. More frequent measures will be taken if there are symptoms, such as chest pain, shortness of breath, or neurological symptoms that may be indicative of hypertension. The therapists will measure subject body temperature approximately every 60 to 90 minutes. The timing of these measurements will be adjusted so that they do not interfere with the therapeutic process.

All AEs and spontaneously reported reactions will be collected, as described in Section 8.5. AEs and spontaneously reported reactions may be collected during face-to-face visits or over the telephone. Common reactions that are spontaneously reported are collected for seven days after each experimental session on a separate CRF page and will be categorized as mild, moderate, or severe.

As an additional safety and support measure, all subjects will be required to designate a family member, close friend, or significant other who knows them well to provide ongoing support for the duration of their active participation in the study. Precedence for the importance of post-session support has been established in earlier similar studies [155]. Responsibilities of the designated support person include:

- Providing reliable transportation, as required, to and from pre- and post-session appointments and participating in study visits, as appropriate.
- Driving the subject home or to another secure location following sessions. No participant will be allowed to drive themselves home after experimental sessions.
- Remaining available to attend to basic comfort needs and to talk with subject in person, by phone, or online for 24 hours post-session.

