5.2.3 Experimental sessions

Subjects will receive two blinded experimental sessions of therapy assisted by MDMA or placebo, scheduled one month apart after integrative sessions are complete. Procedures for drug-assisted therapy will remain the same across all sessions. During experimental sessions, there will be periods of structured and unstructured interactions. The structured interactions will be selected based on elements of therapeutic interventions that are currently in use in this population for the treatment of social anxiety. Structured interactions during experimental sessions are intended to develop the therapeutic relationship between subjects and therapists and to enhance skills of social perception through administration of the TASIT. The unstructured interactions will include an array of therapeutic activities and approaches that would be appropriate for subjects to engage in during experimental sessions. All subjects will follow the same schedule of structured alternating with unstructured periods but will be able to choose from a selection of activities during each unstructured period. Examples include, but are not limited to, working with art supplies, listening to preselected music, writing in journals, silent introspection, and engaging in rapport-building interactions with therapists. The therapists will create and communicate a setting of safety and support the subject during periods of inner focus. Therapists will use a largely nondirective approach. Therapists will provide encouragement for staying present with difficult experiences. Therapists may occasionally offer gentle guidance or redirection as a choice to encourage collaborative exploration if the subject repeatedly avoids interpersonal contact. Therapists will use music to support the experience without being intrusive.

Table 4. Schedule of Procedures for Experimental Sessions

Approximate Time	Procedure or Action
------------------	---------------------

9:00	Urine drug screen and pregnancy test. Subject acclimated to environment, C-SSRS
9:45	Baseline Blood Pressure (BP), Pulse, SUD
10:00	MDMA Administration , begin recording to audio and video
11:00	BP, Pulse, SUD, BT
12:00	BP, Pulse, BT, SUD, During 2 nd exp. session only: Blood draw
12:15	Start TASIT (EET, SM-I, SM-E)
13:00	BP, Pulse, BT, SUD
14:00	BP, Pulse, BT, SUD
15:00	BP, Pulse, BT, SUD
16:00	BP, Pulse, BT, SUD, C-SSRS, General Wellbeing
17:00	BP, Pulse, BT, SUD, End of session

Pre-drug:

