- a. At least 24 hours prior to the first experimental session the subject will be randomized. The PI will obtain the container assignment using a web-based randomization program prior to the blinded sessions.
- b. On the day of the experimental session, the subject will arrive approximately one to one and a half hours prior to drug administration.
- c. Confirm continuing eligibility by reviewing inclusion/exclusion criteria.
- d. Collect information on phase of menstrual cycle for female subjects.
- e. Perform a urine drug screen. A positive drug screen will be reviewed by the PI and may be cause for delaying drug administration to a later time, rescheduling the session to a later date, or withdrawing the subject from the study.
- f. If a woman is of childbearing potential, perform a urine pregnancy test. A positive pregnancy screen is cause for withdrawal from the protocol.
- g. If the subject continues to meet criteria and the subject reports that they followed appropriate rules and restrictions, the session will proceed.
- h. Review procedures for the experimental session with the subject.
- i. Record the entire session to video and audio. Subjects may review video recordings of their experimental sessions upon request.
- j. The session will last for approximately seven hours or longer.
- k. The therapists will administer the C-SSRS prior to drug administration.
- l. Before drug administration, discuss and review the subject's goals, intentions, and concerns and some of the commonly experienced effects of MDMA.
- m. Instruct the subject not to use caffeine or nicotine two hours before or six hours after the dose of drug.
- n. Subject body temperature will be measured at baseline prior to administration of the

- initial dose and approximately every hour after that. The therapists may make more frequent measurements if body temperature exceeds more than 1°C above baseline.
- o. Subjects will complete the SUD at baseline prior to administration of the initial dose. Subjects will complete the SUD every 60 to 90 minutes, until the session is over, allowing a window of up to 30 minutes to fit into the therapy process where a natural break occurs. If necessary, the therapists can make a greater number of measurements, as their clinical judgment dictates.
 - p. Measure BP, pulse, and BT at baseline prior to drug administration.

During:

- q. At approximately 10:00 in the morning, subjects will receive the initial dose of drug along with a glass of water.

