- r. The subject will sit or recline on comfortable furnishings. Eyeshades and a program of music will be provided if the subject wishes to use them. Subjects may speak to the therapists whenever they wish, who will provide guidance and support, as needed.
- s. Measure BP, pulse, and BT once every hour throughout the experimental session. More frequent measures will be taken if clinical signs and symptoms of hypertension are observed. If BP values are sustained at 180 systolic and/or 110 diastolic, the PI will make a decision about whether to conduct additional measurements or to provide treatment. Measurements may be repeated until they have been decreasing for 15 minutes or have stabilized at a level judged by the PI to be safe.
- t. After the first hour, if the subject has not spoken spontaneously, check in with him/her about the nature of the experience. For the rest of the experience, as appropriate, the therapists will support and encourage the subject in emotional processing and resolution of whatever psychological material is emerging.
- u. Approximately two hours after drug administration during the second experimental session, prepare the subject for the blood draw for biomarker analysis. Bring in the phlebotomy technician when the subject is emotionally ready for the blood draw.
- v. Initiate the TASIT. The TASIT administration may be spread out between hours two and three to fit around the therapeutic process.
- w. Record any spontaneously reported reactions during the session.
- x. Provide water and electrolyte containing fluids throughout the session but not to exceed 3 L overall.
- y. Provide food during the latter part of the session.
- z. If it is appropriate to do so, initiate the first question of the C-SSRS at any point in the session if the subject is experiencing significant psychological distress that does not respond readily to processing with the therapists. The C-SSRS is required at least once during the session. It is preferable to administer it towards the end of the session, about six hours after the initial dose.
- aa. End the session if all medical and psychiatric parameters are acceptable and the subject is alert, ambulatory, and emotionally stable.

Post-drug:

- bb. The therapists will depart from the site when they have concluded that the subject is emotionally and medically stable. Therapists shall remain available to subjects during the experimental session and for one week after via 24 hour cellular phone for

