Vital signs

Vital signs (heart rate, body temperature, systolic and diastolic blood pressure) will be summarized using descriptive statistics at baseline and at each post-baseline time point. Occurrences of systolic and diastolic blood pressure, heart rate, and body temperature readings above the pre-determined cutoff will be displayed with numbers and percentages by timepoint.

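### SAP 8.10.4 summarises vital signs only by timepoint and omits the Protocol's peak analysis, so its planned tables cannot by themselves show how many subjects ever crossed a cut-off

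*Protocol*

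**What the plan says.** **When readings are taken.** Table 4 in Protocol 5.2.3 sets a pre-dose reading at 9:45, drug at 10:00, and readings at 11:00 and hourly to 17:00, all as approximate times. Further readings depend on how the subject is doing:

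- Symptoms (5.1.3): "More frequent measures will be taken if there are symptoms, such as chest pain, shortness of breath, or neurological symptoms".
- Signs (5.2.3, item s): "More frequent measures will be taken if clinical signs and symptoms of hypertension are observed".
- High blood pressure (5.2.3, item s): at a sustained 180 systolic and/or 110 diastolic the investigator decides whether to measure again. "Measurements may be repeated until they have been decreasing for 15 minutes", or until they have stabilised at a level judged safe.
- High temperature (5.2.3, item n): therapists may measure more often once it is more than 1 °C above baseline.

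Reading times can also move: "The timing of these measurements will be adjusted so that they do not interfere with the therapeutic process" (5.1.3).

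**How they are analysed.** SAP 8.10.4 plans descriptive statistics at baseline and at each later timepoint, and for blood pressure, heart rate and temperature "readings above the pre-determined cutoff will be displayed with numbers and percentages by timepoint". It gives no cut-off values, denominator, time windows or rule for unscheduled readings. Protocol 12.0 plans something further: a comparison of peak post-drug blood pressure, heart rate and temperature by condition and by MDMA dose. The SAP has no counterpart to it.

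**Temperature.** In 5.1.3: "The therapists will measure subject body temperature approximately every 60 to 90 minutes". In 5.2.3, item n, temperature is taken before the "initial dose and approximately every hour after that". Table 4's 9:45 row reads "Baseline Blood Pressure (BP), Pulse, SUD", with no temperature, whereas items n and p of the same section call for one before drug.

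**The concern.** Protocol 12.0 calls this primarily a safety study and says safety data will help choose the dose for later trials. With 8 MDMA and 4 placebo subjects, the most readable vital-sign result is how many subjects in each group went above a cut-off. A by-timepoint display does not give that number, because the same subject can appear at several hours and different subjects can appear at different hours.

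The unscheduled readings add to the difficulty. They cluster in subjects with symptoms or high values, and the SAP does not say whether they enter the by-timepoint table, under which hour, or how often one subject may count. Two analysts following the SAP could produce different tables from the same data. The Protocol's peak analysis would have covered much of this ground, but the SAP does not carry it over.

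**Working it through.** The documents state no rate or power for vital-sign elevations, so there is no such figure to reproduce. The checks below are counting checks.

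**1. Design counts.** From Table 1: Stage 1 has 8 × 2 = 16 MDMA sessions and 4 × 2 = 8 placebo sessions; Stage 2 adds 4 × 2 = 8 MDMA sessions. The total is 16 + 8 = 24 MDMA sessions, 8 at each dose, which agrees with Protocol 2.3. Table 4 gives 7 scheduled post-dose readings (11:00 to 17:00), so Stage 1 has 16 × 7 = 112 on MDMA and 8 × 7 = 56 on placebo.

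**2. What a by-timepoint table determines.** Read it in the most favourable way: c_t is the number of subjects above the cut-off at timepoint t in one session of 8 MDMA subjects. The number N who were ever above it satisfies max(c_t) ≤ N ≤ min(8, Σc_t).

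| Illustrative counts at the 7 timepoints | Minimum N | Maximum N |
|---|---|---|
| 1, 1, 1, 1, 1, 1, 1 | 1 (12.5%) | 7 (87.5%) |
| 0, 1, 2, 2, 1, 0, 0 | 2 (25%) | 6 (75%) |

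**3. The same in rates.** Assume a probability p of being above the cut-off at each timepoint. The share ever above in a session is p if the same subjects are high throughout, and 1 − (1 − p)^7 if timepoints are independent.

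| Assumed p | Full overlap | Independence |
|---|---|---|
| 2% | 2% | 13.2% |
| 5% | 5% | 30.2% |
| 10% | 10% | 52.2% |

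**4. Unscheduled readings.** Suppose one of 8 subjects is high at one hour and is re-read k times, always high. If repeats are assigned to that hour and readings are counted, the percentage is (1 + k)/(8 + k): 2/9 = 22.2% for k = 1, 4/11 = 36.4% for k = 3, 5/12 = 41.7% for k = 4. If subjects are counted, it is 1/8 = 12.5% whatever k is. The SAP does not say which applies.

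**5. Protocol against SAP.** Protocol 12.0 plans peak values, by condition and by dose. SAP 8.10.4 plans values at each timepoint, with no peak, and its vital-sign paragraph does not name treatment group, although the adverse-event, C-SSRS and SUD paragraphs beside it do.

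**6. A per-subject count.** Each Stage 1 session gives one number out of 8 on MDMA (4 at each of the two doses used in that session) and one out of 4 on placebo. Repeating a high reading does not change it.

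**7. Temperature.** From a 10:00 dose, hourly readings to 17:00 number 7. At the loosest end of 5.1.3, every 90 minutes, they fall at 11:30, 13:00, 14:30 and 16:00, which is 4.

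**The case against.** A reader might infer that the trial report cannot show how many subjects had a large rise. The documents do not support that. Protocol 12.0 plans peak values by condition and dose, SAP 8.0 puts untabulated data in the listings, and with 12 subjects the count can be made by hand from either. Adverse events are also reported by subject in SAP 8.10.4, so some rises may appear there. All of this stands. It does not close the gap: the SAP contains no peak analysis, a comparison of peaks need not report how many subjects crossed a cut-off, a hand count from listings follows no agreed rule, and nothing makes a reading above a cut-off an adverse event.

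It is also tempting to say that readings multiply exactly when values are bad. Value-driven repeats are at the investigator's decision for blood pressure and optional for temperature, and the triggering reading would often be a scheduled one already in the table. Closer monitoring of a symptomatic subject is ordinary safety practice. The fault lies in the analysis rule, not the monitoring.

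The 41.7% in step 4 assumes a denominator of readings, which the SAP never states; its wording may mean subjects at each timepoint. The range in step 2 holds even on that kinder reading.

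On temperature, an interval of 60 to 90 minutes includes hourly, and a baseline and hourly reading is required in 5.2.3 (n, p, s), in the safety objectives of both documents (3.3), and in Table 2's footnotes. The documents therefore do not support an inference that sessions would run without a reference temperature. The inconsistency is editorial.

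**Conclusion.** The point holds as a gap in the SAP. Its only threshold display is by timepoint, it has no rule for unscheduled readings and no count by subject, and it drops the peak analysis in Protocol 12.0. The planned tables alone therefore leave the number of subjects ever above a cut-off undetermined, by as much as 1 to 7 of 8 in the plainest illustration. That range follows from counting alone; the rates in step 3 and the repeat counts in step 4 are assumptions, because the documents give none.

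The data needed are already planned, so this does not threaten the trial or hide results beyond recovery. It should be corrected before analysis because safety is the study's stated main purpose. The temperature discrepancies are minor.

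**What to change.** In SAP 8.10.4:

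1. Carry over from Protocol 12.0 the analysis of peak post-drug blood pressure, heart rate and temperature, by condition and by dose.
2. For each session, by treatment group and dose, report the number and percent of subjects with at least one post-dose reading above each pre-determined cut-off, and print the cut-off values in the SAP. Give the count twice: from all readings, and from scheduled readings only. The all-readings count catches rises between scheduled times but is affected by more frequent reading of symptomatic subjects; the scheduled-only count is not affected in that way but can miss such rises.
3. Restrict by-timepoint summaries to scheduled readings, with stated time windows, and list unscheduled readings separately.

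In the Protocol, reconcile the temperature interval in 5.1.3 with 5.2.3 (n, s) and Table 4, and Table 4's 9:45 row with 5.2.3 (n, p).

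The cost is one or two extra tables and some wording. No new measurements are needed. Scheduled and unscheduled readings must be distinguishable in the data; the case report form was not available, so whether it already allows this should be checked.

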5.1.4 Process Measures

All therapy sessions, including experimental sessions, may be recorded to audio and video, with all recordings preserved for research and training purposes.

Belief of condition assignment and certainty will be collected from each therapist responsible for treating the subject and the subject at the integrative session on the day after each blinded experimental session in Stage 1. These beliefs are collected as a part of the sponsor's ongoing initiative to optimize the blinding of MDMA-assisted therapy.

The Feedback Questionnaire has been developed internally by the sponsor to assess perceived benefits and harms of MDMA-assisted therapy, feedback on therapeutic

methods, and prior treatments received. The questionnaire will be completed as a self-report measure and then reviewed with the subject in order to ask follow-on questions during a semi-structured qualitative interview, which may be video recorded. This questionnaire will be completed at baseline and at the 6-month follow-up visit.

5.2 Study Procedures and Visit Descriptions

5.2.1 Prescreening and Screening

The therapist team for this study will consist of the PI, [name]., and co-investigator [name]. Candidate, and all study visits will be completed at Harbor-UCLA Medical Center. Prospective subjects will be prescreened by telephone or email according to an IRB-approved script to learn if they meet basic eligibility criteria. All individuals who are prescreened should be assigned a screening number and recorded on the Subject Screening Log where information on the selection of potential subjects in the trial should be collected.

Upon signing the IRB-approved informed consent form (ICF), the potential subject may commence study-related screening activities. The screening number should also be recorded on the signed ICF. If a subject is enrolled, the study staff should record the enrollment date and assign a subject number. If a subject is not enrolled, an explanation should be recorded on the Screening Log. A CRF will not be completed for subjects who are not enrolled. These subjects will only be documented on the Screening Log and Source Records. It is the responsibility of the PI to file the Screening Log in the investigator site file (ISF) to be readily available for on-site monitoring and/or inspection by relevant authorities. Screening may take place over more than one day and should be complete by up to two months prior to enrollment. If, after reviewing all information, the PI concludes that a subject is eligible, they will enroll the subject in the study. Visits will be scheduled consecutively, as described in the Time and Events Table.

- a. Explain and obtain written informed consent from the subject and Support Partner. Written informed consent must be obtained from the subject prior to performing any tests or evaluations for the study.
- b. Assign the subject a screening number. Complete the Screening Log.
- c. Review the ability of females of childbearing potential to become pregnant and their commitment to practice appropriate birth control, as determined by the PI for the treatment period of the study.
- d. Collect perceptions about the study using the Feedback Questionnaire.
- e. Administer C-SSRS to assess suicide risk.
- f. Administer the SCID-I-RV to assess co-morbid psychological disorders.
- g. Administer ADOS-2, Module 4 to confirm autistic status.
- h. A blinded IR will administer the LSAS.
- i. Obtain medical and psychological history by interview.
- j. Collect symptoms at baseline specific to the study population.
- k. Collect information on pre-study and current medications.

- l. Perform a general physical examination. The examination will involve the following procedures:
 - Blood pressure
 - Pulse
 - Height
 - Weight
 - Body temperature
 - Examination of head, eyes, ears, nose, throat, skin, heart, lungs, abdomen, and extremities
 - Brief neurological exam (cranial nerves 2-12, sensory, motor, reflexes, and cerebellar function)
 - Urine-dip pregnancy test on females with childbearing potential
 - Urinary drug test
- k. Conduct Electrocardiogram (ECG/EKG)
- l. Collect information on phase of menstrual cycle for female subjects.
- m. Collect samples for clinical lab assessments, including:
 - Blood for screening clinical lab assessments (see Section 10.1)
 - Blood for baseline OT,AVP, and CORT analysis (see Section 10.2)

Results of HIV serology will be kept confidential and appropriate referral for counseling may be necessary in accordance with state law. The clinical laboratory values will be used to establish eligibility and will be kept with the subject's Source Record. The clinical laboratory values will not be captured in the CRF, but will be used to establish eligibility and will be kept with the subject's Source Record. Clinically significant abnormal values will be captured as medical history. If, upon examination, there are questions raised about possible medical problems, the PI will request a review of subject medical records and request additional tests or assessments, as indicated.

